# 3.10 Follow-up and Retention

Follow-up assessments will be conducted with patients and caregivers at 12 weeks, and with caregivers at bereavement (12 weeks or later after patient's death). To enhance retention, we distribute contact cards with the contact information for study staff, mail reminder cards, mail answer guides prior to telephone assessments, and send condolence cards to referred family caregivers when a patient dies. Our data collection strategy is designed to minimize participant burden by using parsimonious measures previously pilot-tested with this population, administering patient and caregiver interviews by phone, and providing compensation. Enrolled patients and caregivers will be paid \$25 each upon completion of the 12-week follow-up assessment, if applicable.

Enrolled patients and caregivers will be paid an additional \$25 each if asked to complete the qualitative in-depth interview.

#### 3.11 Withdrawal

Participants may withdraw from the study at any time. All previously collected information will continued to be used for study purposes until study completion. For participants who wish to withdraw, we will ask them why. For participants who do not have a response to this open-ended question, we will offer a list of reasons for withdrawal from previous studies (e.g., not enough time, no longer interested, no benefit, etc).

# 4. MEASURES AND ASSESSMENTS

#### 4.1 Overview

Successful ACP influences multiple important outcomes. We selected priority outcomes related to patients, caregivers, and healthcare utilization based on an organizing framework developed by an international panel of ACP experts. We focused on outcomes for which validated and parsimonious measures have been developed for use with seriously-ill participants. We chose a 12-week time-point for patient and caregiver assessments to balance the need to allow sufficient time for ACP to occur without incurring excessive loss to follow up in a seriously-ill population. For patients who die during the study period, we will conduct brief additional interviews with bereaved caregivers 12 weeks or later after a patient's death, allowing assessment of EOL care and caregiver bereavement adjustment while minimizing participant burden. Additionally, we will review medical records for documented care goals and EOL healthcare utilization.

# 4.2 Primary Outcome

We chose patient-reported engagement in ACP as our primary outcome because this validated measure reflects a patient- and caregiver-centered understanding of ACP as a complex process involving multiple behaviors, rather than simply completion of an advance directive. Importantly, the 15-item version of the ACP Engagement Survey measures a broad range of ACP behaviors, is able to detect change in response to ACP interventions, and can be administered with minimal participant burden.

#### 4.3 Secondary Patient and Caregiver Outcomes

We will additionally measure ACP discussions with caregivers, ACP discussions with clinicians, and AD completion (using both a single question and by reviewing medical records for any new ACP documentation). For patients who die during the study period, we chose caregiver-reported measures of goal-concordant EOL care because these validated measures capture overall receipt of goal-concordant care in the last month of life and incorporate the perspectives of bereaved family members. In contrast, measuring receipt of goal-concordant EOL care based on chart review does not account for frequently-encountered situations in which documented ADs do not reflect the

current, real-time clinical scenario. Similarly, we chose a validated, caregiver-reported measure of quality of EOL care because cancer caregivers provide an important and reliable perspective on this outcome. We include measures of caregiver depression, anxiety, and post-traumatic stress symptoms because many patients cite easing the burden on families as a motivator of ACP and it is possible that family caregivers may experience less distress after participating in a facilitated ACP intervention.

	/ Caregiver Outcomes (Aim 1)	II - ·
Specific Measure	Description	Timing
ACP Engagement (primary outcome)	15-item ACP engagement survey assessing ACP processes related to choosing a medical decision maker, discussing and documenting preference for care at EOL, flexibility for surrogate decision making, and asking questions of medical providers. Single summary score (range 0-5 with higher scores indicating higher engagement) has high internal consistency (Cronbach's alpha=0.92) and responsiveness to change. 	Baseline, 12 weeks
ACP discussions with caregivers	"Have you talked with your family or friends about the kind of medical care you would want if you were very sick or near the end of life?" 27, 30, 31	Baseline, 12 weeks
ACP discussions with physicians	"Have you talked with your doctor about the kind of medical care you would want if you were very sick or near the end of life?" 27, 30, 31	Baseline, 12 weeks
AD completion	Single question will assess AD completion. We will additionally assess documented care goals by reviewing medical records for any new ACP documentation, including AD forms or documented discussion.	Baseline, 12 weeks
Receipt of goal- concordant EOL care	Two validated caregiver-reported questions have been used to measure receipt of goal-concordant EOL care for patients with cancer: (1) "In your opinion, to what extent were [the patient's] wishes followed in the medical care received in the last month of life?"; and (2) Caregivers asked about patient's preferred and actual places of death, with questions separated in the survey to minimize conscious comparison. 	Bereavement
Quality of EOL care	The Caregiver Evaluation of Quality of End-of-Life Care (CEQUEL) scale is a 13- item instrument (range of scores 13-26) with demonstrated reliability and convergent validity among cancer caregivers. Strengths include brevity and clinical relevance, with inclusion of 4 distinct but related factors (prolongation of death, perceived suffering, shared decision-making, and preparation for death) associated with caregiver bereavement outcomes. 	Bereavement

Depression and anxiety symptoms	Hospital Anxiety and Depression Scale (HADS) is a widely-used 14-item instrument measuring symptoms of depression and anxiety. $^{33}$ It has been extensively validated for screening emotional distress among advanced cancer patients $^{34}$ and family members. $^{35}$ Score of $\geq$ 8 on either domain indicate significant symptoms of depression or anxiety with good sensitivity and specificity. $^{36}$	Baseline, 12 weeks, Bereavement
Post-traumatic stress symptoms	Impact of Events Scale is a 22-item self-report instrument for PTSD symptoms with 3 subscales measuring intrusion (8 items), avoidance (8 items) and hyperarousal (6 items). Subscales have high internal consistency (Cronbach's alpha ranging from 0.79-0.92). A score of 30 or higher is considered a clinically significant burden.	Bereavement

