#### PROTOCOL SUMMARY

**Title:** Patient-centered and efficacious advance care planning in cancer: the

PEACe-compare trial

**Précis:** PEACe-compare is a single-blind, patient-level randomized trial to

compare the effectiveness of facilitated ACP vs web-based ACP among

patients with advanced cancer and their family caregivers.

**Objectives:** Aim 1: To compare the effectiveness of facilitated ACP versus web-

based ACP on patient and family caregiver outcomes.

Aim 2: To assess implementation costs and the effects of facilitated ACP and web-based ACP on healthcare utilization at end of life. Aim 3: To identify contexts and mechanisms that influence the effectiveness of facilitated ACP versus web-based advance care

planning.

**Population:** 400 adult patients with advanced cancer and their caregivers

Sites: The study will be conducted at UPMC Hillman Cancer Center clinics in

Western Pennsylvania.

Description of Interventions:

Facilitated ACP will be conducted using the Respecting Choices® facilitated ACP conversation model. Patients randomized to this arm will participate in an in-person or remote (telephonic or video) facilitated ACP discussion led by a trained facilitator using a structured interview tool designed for adults with chronic, incurable illness.

Web-based ACP will use the PREPARE for Your Care tool, an online ACP tool that includes 5 ACP steps using interactive videos. Patients randomized to this arm will view PREPARE on a home computer or on

a tablet in the oncology office.

**Study Duration:** 5 years

Subject Participation

**Duration:** up to 5 years

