## 3.2 Eligibility Criteria

We designed patient eligibility criteria to be broadly representative of the population with cancer for whom ACP is most important. There are no inclusion or exclusion criteria based on gender, race, or ethnicity. There is a lack of good evidence regarding the optimal timing of ACP in advanced cancer, but in most prior studies patients and clinicians preferred to delay the introduction of ACP to later in the illness trajectory rather than at the time of diagnosis. The validated 'would not be surprised' question is a simple and effective method for identifying patients with cancer at high risk of dying in one year (hazard ratio 7.8). We do not include patients with hematologic malignancies because these diseases have very different trajectories and treatment options near the end of life,  and the majority of patients seen at participating practices have solid tumors. We include patients who have previously completed an AD because preferences change and patients may benefit from additional engagement in ACP with changing health contexts. We exclude patients < 18 because children with incurable cancer have unique ACP needs best served by clinicians experienced working with pediatric populations, and our study is conducted at adult oncology practices. Our teach-back method for informed consent is designed to ensure complete comprehension among vulnerable populations.

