# 5.2 Primary and Secondary Outcomes

All analyses for treatment group comparisons will use an intention-to-treat approach.

The primary outcome is ACP engagement. We will test the effect of treatment assignment on the primary outcome using linear mixed models. The model will include treatment group, and baseline ACP engagement as fixed effects. To adjust for possible clustering of patients seen by the same facilitator or provider, we will include random effects for facilitators (for patients in the facilitated ACP group only) and oncologists.

The same analytic approach will be used for secondary outcomes: perceived quality of EOL care and caregiver symptoms of anxiety, depression and PTSD. Binary outcomes such as ACP discussions, AD completion, documented care goals, and receipt of goal-concordant EOL care will be compared using mixed effect logistic regression with the same set of fixed effects and random effects as in the models for continuous outcomes. We will also compare the rates of completion of intervention between the two intervention groups, using the same model as for other binary outcomes.

Analyses of health care utilization data will use GLMM (generalized linear mixed model), with logit link (binary distribution) for dichotomous (yes/no) health care outcomes such as chemotherapy within last 2 weeks of life. Again, we will use intervention group and baseline ACP as fixed effects and oncologist and clinic as random factors.

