#### 5.5 Sample Size and Power Calculations

We selected our sample size to provide ample power to assess differences in the primary outcome—ACP engagement—as well as secondary patient, caregiver, and healthcare utilization outcomes. All calculations were conducted using  $\alpha$ =0.05, based on two-sample t-tests for continuous outcomes and chi-squared tests for binary outcomes. To adjust for possible clustering effect within each oncologist, we used the design effect (DE=1+[(1+CV²)m-1)] $\rho$ ), where CV=the coefficient of variation for cluster size and m=the number of patients per oncologist. Conservatively estimating a 25% loss

to follow-up for patient-reported outcomes, our sample size will provide >98% power to detect a moderate effect size (Cohen's d=0.5) in our primary outcome—ACP engagement. While any increase in ACP engagement may be associated with clinically meaningful improvements in EOL outcomes, a minimal clinically important difference has not been established. A moderate effect size (0.35 on a 5-point score, based on a SD of 0.7),27 ensures that we will be able to detect a difference comparable to the changes seen with ACP interventions in prior trials. We will have >78% power to detect a 15% difference in rates of ACP discussions with family and physicians between groups (assuming discussion rates of 25% in the web-based arm) and >99% power to detect a 20% difference in rates of AD completion (assuming an AD completion rate of 50% in the web-based ACP arm). Power is similarly adequate for all caregiver-reported outcomes, assuming a 75% caregiver participation rate and 15% loss to follow-up, which results in an effective sample size of 254. For caregiver-reported quality of EOL care we will have 97.6% power to detect a moderate effect size, and for caregiver anxiety and depression we will have 83.2% power to detect a clinically meaningful difference (Cohen's d=0.368).59 Anticipating that 90% of patients will die during the study period (resulting in an effective sample size of 360), we will have >73-78% power to detect an 8% absolute decrease in ICU admissions and chemotherapy use at the EOL and >80% power to detect a 15% decrease in no hospice or hospice ≤ 3 days before death, based on national data.

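### The 4.3 text measures AD completion by question plus chart review, but the 4.3 table, 4.1 and 5.2 keep the chart review as a separate outcome; on the question alone the stated power is about 95%, not >99%

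*Combined protocol and SAP*

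**What the plan says.** AD completion is an Aim 1 outcome (section 2). The places that bear on its definition are these.

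- **4.3, text:** the secondary outcomes include "AD completion (using both a single question and by reviewing medical records for any new ACP documentation". Nothing says whether one positive source is enough, both are needed, or one overrides the other.
- **4.3, table, AD completion row:** "Single question will assess AD completion". The row continues: "We will additionally assess documented care goals by reviewing medical records for any new ACP documentation, including AD forms or documented discussion".
- **4.1:** medical records are to be reviewed for documented care goals and end-of-life utilization.
- **5.2:** mixed-effects logistic regression is planned for "Binary outcomes such as ACP discussions, AD completion, documented care goals, and receipt of goal-concordant EOL care". AD completion and documented care goals are two entries in that list.
- **5.5:** more than 99% power is claimed for a "20% difference in rates of AD completion (assuming an AD completion rate of 50% in the web-based ACP arm". The source of the AD measure is not stated. The 25% loss to follow-up is given for patient-reported outcomes.
- **3.2:** "We include patients who have previously completed an AD because preferences change". An AD that predates the trial is therefore possible at entry.

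**The concern.** The logistic model in 5.2 needs one yes or no per patient, and the 4.3 text and table can give different answers for the same patient.

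- **Who counts.** A clinician's note of a discussion, with no AD form, is new ACP documentation. It could count as AD completion under the text. Under the table it counts only towards documented care goals.
- **Double counting.** Under the text, the same chart entry could score in both outcomes, although 5.2 tests them as separate outcomes.
- **Prior ADs.** A patient with an old AD may answer yes (the question's wording is not given) while the chart holds nothing new.
- **Denominator.** The question needs the 12-week interview. Chart review does not, and could reach more patients.
- **Arm dependence.** Under 3.5, facilitators help complete the AD and upload it to the record when appropriate. Web-arm patients receive a copy of the form, and no upload help is described. A chart component may therefore respond to the arm in a way that the question does not.

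At stake are the event rates in a named secondary outcome and the power claim attached to it. If the choice is left until the data are seen, the result could depend on it.

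**Working it through.** **Inputs from the documents.** 400 patients (Protocol Summary), randomised 1:1 (3.6); alpha 0.05, chi-squared test for binary outcomes, 25% loss for patient-reported outcomes, 50% in the web arm and a 20-point difference, hence 50% versus 70% (5.5). Sidedness is not stated; two-sided is assumed.

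**Sample sizes.** Question: 400 × 0.75 = 300, or 150 per arm. Chart: at most 400, or 200 per arm.

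**Formula.** With n per arm and pooled rate p̄ = (0.50 + 0.70)/2 = 0.60,

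power = Φ{ [0.20 − 1.96 × √(2 × 0.60 × 0.40 / n)] / √[(0.50 × 0.50 + 0.70 × 0.30) / n] }

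**The plan's figure (>99%).**

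- n = 150: (0.20 − 1.96 × 0.05657) / 0.05538 = 1.609, power **94.6%**.
- n = 200: (0.20 − 1.96 × 0.04899) / 0.04796 = 2.168, power **98.5%**.
- Other versions at n = 150: unpooled 95.1%, arcsine 94.6%, continuity-corrected 93.2%, one-sided 97.3%.
- Two-sided 99% power needs 216 per arm, or 432 patients, more than the trial enrols. Only a one-sided test on all 400 with no design effect passes 99% (99.4%).

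**Cross-check on neighbouring figures.** At 150 per arm, ACP discussions (25% versus 40%) give 79.5% against the stated >78%, and the primary outcome (d = 0.5) gives 99.1% against >98%. Both fit the interviewed sample. The AD figure does not.

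**Design effect.** Section 5.5 gives the formula 1 + [(1 + CV²)m − 1]ρ but no values. Assumed range, with CV = 0:

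| m | ρ | Design effect | Power, 300 | Power, 400 |
|---|---|---|---|---|
| none | none | 1.00 | 94.6% | 98.5% |
| 5 | 0.01 | 1 + 4 × 0.01 = 1.04 | 93.8% | 98.2% |
| 20 | 0.02 | 1 + 19 × 0.02 = 1.38 | 85.8% | 93.9% |

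The plan's own discussion figure suggests the small end. Power of 78% there needs 145 per arm, so starting from 150 the design effect can be at most 150/145 = 1.03. At 145 per arm, AD power is 93.9%.

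**Definitions side by side.**

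| Patient at 12 weeks | 4.3 table | 4.3 text |
|---|---|---|
| Answers no; new charted discussion, no AD form | No | Yes if either source counts; no if both are needed |
| Answers yes from an AD before the trial; no new documentation | Yes | Yes if either source counts; no if both are needed |
| Not interviewed; new AD form in chart | Missing | Yes if either source counts; otherwise undetermined |

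**The case against.** The strongest reply is that the document largely settles the matter. The table, 4.1 and 5.2 all keep chart review apart from AD completion. The one outlier is a parenthesis in a rationale paragraph, and it can be read as shorthand for a table row that holds both measures. No section proposes a composite. This carries weight: it is why the fix follows the table, and why the point is a conflict to reconcile and not a missing definition. It does not remove the conflict, because the text says that both sources are used and the loose reading still gives no combining rule.

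It is also fair that the denominator alone moves power by only 98.5 − 94.6 = 3.9 points, that the outcome is secondary, and that 400 is an upper bound for charts. Section 3.9 does not say whose charts are read or over what window, and 3.11 covers only information collected before withdrawal.

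A reader might infer that a composite would dilute the difference and cost much of the power. The documents do not support that. They give neither a composite rule nor a charting rate, and the direction turns on an assumption about the arms. Suppose either source counts, with 150 per arm, and 20% of those answering no have a new note in both arms. The rates become 0.50 + 0.50 × 0.20 = 60% and 0.70 + 0.30 × 0.20 = 76%, a 16-point difference with 84.7% power. If the facilitated share is 40% instead, that arm becomes 0.70 + 0.30 × 0.40 = 82%, a 22-point difference with about 99% power.

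**Conclusion.** The conflict is real and should be corrected. The 4.3 text is out of line with the 4.3 table, 4.1 and 5.2. Following it could count a charted discussion as an AD, use one chart finding in two outcomes, and bring in a source that may differ by arm. The direction of any effect on the treatment difference is unknown.

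On the table's definition, power is about 95% before any design effect. This rests on a two-sided 0.05 test, 150 per arm, and 50% versus 70% being rates for the question. Under the assumed design effects of 1.04 to 1.38 it is 93.8% to 85.8%.

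Two further inferences go too far. One is that the trial is underpowered for AD completion: about 95% is ample, and what fails is the stated bound. The other is that >99% shows the calculation was made on a chart-based definition with all 400 patients. The two-sided result on 400 (98.5%) lies closer to the claim but still misses it, and 5.5 does not say which source or sample was used.

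**What to change.** 1. **4.3 text.** Change the parenthesis to match the table and 5.2: AD completion is the patient's answer to the single question at 12 weeks; documented care goals is the chart review, analysed separately. State that a chart finding does not alter the AD completion value.
2. **Denominators.** State them for each outcome: patients interviewed at 12 weeks for the question, and randomised patients whose charts are reviewed for documented care goals.
3. **5.5.** State that 50% versus 70% refers to the question. Replace >99% with about 95% (94.6% at 150 per arm, two-sided 0.05, before any design effect), or give the adjusted figure together with m, CV and ρ.
4. **Reporting.** Show agreement between question and chart descriptively, by arm.

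The cost is a few sentences and no new data. The downside is that AD completion then rests on self-report by patients who cannot be blinded (3.7), and it may include ADs that predate randomisation. The model in 5.2 adjusts for baseline ACP engagement, not baseline AD status. The chart outcome should therefore stand beside it in the results. The AD completion row of the 4.3 table also lists a baseline assessment, so the 12-week answers can be tabulated by baseline answer.

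### The two ACP-discussion items have no look-back and the planned model omits the baseline answer to the same item, so earlier talks dilute the 12-week contrast and repeat talks go unseen

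*Combined protocol and SAP*

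**What the plan says.** The outcome table in Section 4.3 gives two yes/no discussion items. One begins "Have you talked with your family or friends about the kind of medical care you would want", the other "Have you talked with your doctor about the kind of medical care you would want". Neither refers to enrolment, randomisation or any other time frame. The timing entry for both is "Baseline, 12 weeks".

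Section 5.2 analyses these binary outcomes by "mixed effect logistic regression with the same set of fixed effects and random effects as in the models for continuous outcomes". For the continuous outcomes, "The model will include treatment group, and baseline ACP engagement as fixed effects". The baseline answer to the discussion item is not listed, and no outcome of new discussion (no at baseline, yes at 12 weeks) is defined.

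The chart review is treated differently. Listed under AD completion, it consists of "reviewing medical records for any new ACP documentation, including AD forms or documented discussion", so the plan separates new from old there.

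Patients with earlier planning are eligible. Section 3.2 states: "We include patients who have previously completed an AD because preferences change and patients may benefit from additional engagement in ACP".

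Section 5.5 claims more than 78% power for a 15-point difference in discussion rates, "assuming discussion rates of 25% in the web-based arm". It does not say whether that rate means new discussions or all yes answers at 12 weeks.

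**The concern.** A patient who talked with family or a doctor before enrolment can truthfully answer yes at both interviews. That 12-week answer carries no information about the intervention. Two things follow.

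- **Dilution.** Baseline-yes patients add equally to the yes count in both arms and shrink the arm difference. The planned covariate, the baseline engagement score, is only a proxy for the answer that matters.
- **Unseen repeat talks.** Section 3.2 includes prior AD completers because they may gain from further planning. An AD does not prove that a talk took place, but any of these patients who had already talked cannot show a further talk on these items.

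Discussions with caregivers and clinicians are named outcomes of Aim 1 (Section 2). If many patients had already talked, a small arm difference could mean either that the interventions perform alike or that few patients had room to change.

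**Working it through.** **Inputs.** 400 patients randomised 1:1 (Sections 3 and 3.6); 25% loss for patient-reported outcomes, chi-squared test, alpha 0.05, and 25% versus a 15-point difference, so 40% (all Section 5.5). I assume a two-sided test, since sidedness is not stated. Evaluable per arm: 400 × 0.75 / 2 = 150. The baseline-yes share *b* is not in the documents; I assume a range and take it as equal in both arms.

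**Formula.** With p̄ the mean of p1 and p2, power = Φ{[|p2 − p1| − 1.96·√(2p̄(1−p̄)/n)] / √[(p1(1−p1) + p2(1−p2))/n]}.

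**The plan's own figure.** p1 = 0.25, p2 = 0.40, n = 150, p̄ = 0.325:

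- 1.96 × √(2 × 0.325 × 0.675/150) = 0.1060
- √[(0.1875 + 0.24)/150] = 0.0534
- (0.15 − 0.1060)/0.0534 = 0.824, so power = 79.5%

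This agrees with the stated figure of more than 78%. A design effect of about 1.04 gives 78%; Section 5.5 does not give the values behind its own design effect. The figures below use none.

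**Reading A: 25% and 40% are rates of new discussion among baseline-no patients.** The 12-week yes rate in an arm is then b + (1 − b)r, and the observed difference is (1 − b) × 15 points. At b = 25% the rates are 0.25 + 0.75 × 0.25 = 43.75% and 0.25 + 0.75 × 0.40 = 55%, a difference of 11.25 points. The alternative analysis keeps 25% versus 40% but uses only the 150 × (1 − b) baseline-no patients per arm.

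| Assumed b | Observed difference (points) | Power, crude 12-week comparison | Baseline-no patients per arm | Power, baseline-no analysis |
|---|---|---|---|---|
| 0% | 15.0 | 79.5% | 150 | 79.5% |
| 10% | 13.5 | 66.9% | 135 | 75.2% |
| 25% | 11.25 | 49.5% | 112.5 | 67.3% |
| 40% | 9.0 | 35.4% | 90 | 57.6% |
| 50% | 7.5 | 27.8% | 75 | 50.0% |

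At b = 25% the crude comparison loses 79.5 − 49.5 = 30.0 percentage points of power, and the baseline-no analysis recovers 67.3 − 49.5 = 17.8 of them. At b = 50% it recovers 50.0 − 27.8 = 22.2 of 79.5 − 27.8 = 51.7.

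**Reading B: 25% and 40% are the yes rates at 12 weeks.** Power for the 12-week comparison is 79.5% whatever b is. With full carry-over, b cannot then exceed 25%. The implied new-discussion rates are (0.25 − b)/(1 − b) and (0.40 − b)/(1 − b):

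- b = 10%: 16.7% versus 33.3%, 135 per arm, baseline-no power 89.0%
- b = 20%: 6.25% versus 25.0%, 120 per arm, baseline-no power 98.3%

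For every positive share computed, under either reading, the baseline-no analysis has more power than the crude 12-week comparison. The crude comparison is a simplification: the planned model also adjusts for the engagement score, which may recover part of the loss. The documents do not allow that part to be quantified.

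**The case against.** The strongest reply is that the share of patients who have had the conversation by 12 weeks is a legitimate endpoint, that it is secondary, and that Section 5.5 most naturally gives the rate on the outcome as measured. On that reading the power statement is right. New activity is also covered elsewhere: the primary engagement score includes discussing preferences, and the chart review looks for new documentation. All of this stands, with two limits: Section 5.5 does not say which rate is meant, and chart review cannot be relied on for talks with family.

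A reader might infer that old and new discussions cannot be told apart at all. The documents do not support that. The same item is asked at baseline, before randomisation (Section 3.6), so a baseline no followed by a 12-week yes marks a first discussion, subject to recall error. Only repeat talks in baseline-yes patients are lost.

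A reader might also infer a biased comparison or an uninterpretable null result. Randomisation balances earlier talks on average, so the effect is dilution and lost power.

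Nor is a look-back question free of problems. Facilitated visits include the health care agent, when available, and other family the patient wishes to bring (Section 3.5). A yes to the family item could therefore partly record attendance at the session.

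Finally, contacts follow standardised scripts (Section 3.8) that are not in the documents. A spoken time frame cannot be excluded; if there is one, the protocol should state it.

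**Conclusion.** The point holds in a limited form. As printed, the items let earlier talks carry into the 12-week answer. The planned model does not use the baseline answer that would deal with most of this, and repeat talks in baseline-yes patients cannot be seen. The result is dilution, not bias.

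Its size is conditional. Under the new-discussion reading, crude power at 150 per arm is 66.9%, 49.5% or 27.8% at assumed baseline-yes shares of 10%, 25% or 50%. Under the 12-week-rate reading, the stated power is unaffected. The tempting conclusion that the power claim in Section 5.5 is wrong is not supported: it reproduces, and the documents give neither the baseline share nor the definition of the 25%.

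The figures assume full carry-over of a baseline yes, equal shares and equal loss in both arms, a two-sided test and no design effect. A change is worth making because the main remedy uses data already collected.

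**What to change.** Before database lock (Section 5.4):

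1. In Section 5.2, add the baseline answer to each discussion item as a fixed effect in the model for that item.
2. Add a pre-specified analysis of new discussions among baseline-no patients. The subgroup is defined before randomisation, so the comparison stays randomised. It also serves as the fallback if nearly all baseline-yes patients say yes again and the logistic model cannot estimate the covariate's coefficient.
3. In Section 5.5, state whether the 25% is a rate of new discussions or of yes answers at 12 weeks.

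These steps need no new data, only an amendment to the analysis text.

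Where 12-week interviews remain, add a version of each item that asks about talks since joining the study. Word it to exclude talks held within the study's own ACP session, and use it as a supporting outcome. Keep the printed items at both times. The cost is two extra yes/no questions, a minor amendment, and a look-back measure available only for the later interviews.
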